## **F. Data Analysis Plan:**

Aim 1: To evaluate the feasibility and acceptability of a multi-component novel weight loss intervention delivered in a WIC setting to a population of low-income, predominantly racial/ethnic minority, obese, postpartum women.

- The RA will transcribe the audiorecorded responses to open-ended questions posed to participants and WIC staff on acceptability. We will use a thematic analytic approach to analyze the data. After reading and discussing all responses amongst team members, we will create a list of codes. We will then use an iterative process to revise codes as needed and identify main themes. We will use a software program (Atlas.ti) for coding. We will assess the ease of recruiting women for the study (number enrolled/number approached) and attrition from the study. We will also calculate the intervention adherence measures, including number of women who received the entire intervention, number of women who came to all visits, participation in self-monitoring, use of phone coaching, and use of the Facebook page. For the Facebook page, we will count the number of posts/individual and categorize the content based on the type of content we see.

Aim 2: To evaluate differences in diet, physical activity, self-efficacy, eating stimulus, and weight change between intervention and control participants to determine preliminary intervention efficacy over a 12-week period.

- We will conduct a univariate analysis of variables to evaluate for baseline group differences, distributions, and outliers for demographic, lifestyle and infant feeding variables. Student t-tests will be used to test for differences between intervention and control groups in change in weight (baseline to 12 wks) and in lifestyle habits using a 2-tailed  $\alpha=0.05$  for statistical significance. [name] will conduct the analysis in consultation with the Child Health Research Biostatistical Core.

Sample Size: This is a feasibility trial, hence, we will not be powered to detect all clinically significant findings. The sample size was chosen based on the sample needed to achieve Aim1. The sample size is 40 (20 intervention and 20 control). We are asking for a sample size in the application up to 80 in case we have a large number of individuals enroll but not participate in the substudy. Given that this is a feasibility trial, we are unsure how difficult recruitment will be.

**G. Summarize Knowledge to be Gained:** We will learn whether the proposed intervention is feasible and acceptable, which will inform future efforts to design weight loss interventions in WIC settings. If it is feasible and acceptable, then this will support the need to evaluate this intervention on a larger scale. Findings from Aim 2 will help us to understand whether the intervention has an impact on lifestyle changes and weight. Again, this is important for understanding whether we should evaluate this intervention on a larger scale, and will inform sample size estimates for future work.

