##### **Secondary:**

- Dietary saturated fat, trans fat, total sugars, "added sugars", fruit and fruit juice, vegetable intake, glycemic load and glycemic index
- Physical activity
- Self-efficacy related to diet and exercise
- Readiness to change
- Eating stimulus index

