- Participant in the lifestyle group in the Main study presenting for 12 week visit
- Participated in Part A Phase 1

Exclusion criteria:

- None

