### Substudy:

The substudy will be broken into 2 parts: Part A for Lifestyle group participants and Part B for the Observation group participants. Data collection varies slightly between these 2 groups as outlined in the study procedures. Only persons participating in the Main study are recruited to be in the Substudy. Screening for eligibility will be done by the PRA based on assigned group in the Main study. Enrollment will occur as follows:

Part A for lifestyle group involves completing 2 phases.

Part A: Phase 1 (labeled Part A.1) involves survey data collection around the time of the Main study's Baseline visit. This will occur either at the visit when the person is consented into the main study or at the baseline visit. After the person is consented into the main study and randomized to the lifestyle group, they can then complete data collection for the main study. Once this is done, they will then be offered the opportunity to participate in this substudy. If they are interested, the RA will conduct informed consent using the information sheet Appendix F.A.1.

Part A: Phase 2 (labeled Part A.2) involves survey and interview data collection at the Main study's 12 week visit. After completing data collection for the Main study at the 12 week visit, the PRA will introduce this study opportunity. If the person is interested, the RA will then complete informed consent, using the information sheet Appendix F.A.1., and enroll the person into the study.

These 2 phases will be presented to participants at these different time points in order to ensure that the substudy opportunity is not an incentive to participate in the main study.

Part B for the observation group involves survey data collection at both the baseline and 12 week visit. This substudy opportunity for data collection at 2 time points will be offered to participants at the baseline visit. If the person is interested, the RA will then complete informed consent, using the information sheet Appendix F-B, and enroll the person into the study.

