- a. Diet Survey: We will use the Block Fat/Sugar/Fruit/Vegetable Screener which takes 10-12 minutes to complete and is available in English and Spanish. This is a publically available questionnaire. This screener contains 55 questions. Portion size is asked for 32 food items. A series of "adjustment" questions ask about usual intake of low-fat/trans-fat free or low-carbohydrate/low-sugar versions of various foods. Analysis produces estimates of saturated fat, trans fat, total sugars, "added sugars" (in sweetened cereals, soft drinks, and sweets), fruit and fruit juice, vegetable intake, glycemic load and glycemic index. The bilingual research assistant will orally administer this. Data will provide estimates on dietary saturated fat, trans fat, total sugars, "added sugars" (in sweetened cereals, soft drinks, and sweets), fruit and fruit juice, vegetable intake, glycemic load and glycemic index. The Block booklets will be mailed to the company for analysis. The only identifier on each booklet will be the participant study ID number.
- b. Pregnancy Physical Activity Questionnaire: We will use a slightly adapted version of the Pregnancy Physical Activity Questionnaire (PPAQ) Chasan-Taber L, Schmidt MD, Roberts DE, Hosmer D, Markenson G, Freedson PS. Development and Validation of a Pregnancy Physical Activity Questionnaire. Med Sci Sports Exer 2004 36(10):1750-1760.
- c. Self-efficacy regarding diet and exercise: some items are from another study (unpublished) and some are from [http://sallis.ucsd.edu/measure\\_selfefficacy.html](http://sallis.ucsd.edu/measure_selfefficacy.html)
- d. Eating Stimulus Index: <http://europepmc.org/abstract/med/19699840>
- e. Readiness to Change: Items are from another study

Participants from the observation group will receive at the 12 week visit a \$50 gift card for their participation.

Overview of data collection:

Data to be collected from study participants and when the data are to be collected

Variable	Baseline Visit 1	4 week visit (Lifestyle group only)	8 week visit (Lifestyle group only)	12 week visit
Main study				
Demographics Questionnaire	X			

Smoking status	X			X
Breastfeeding history	X			X
Health questions	X			X
Weight	X	X	X	X
Height	X			
Substudy				
Block Fat/Sugar/Fruit/Vegetable Screener	X			X
Pregnancy Physical Activity Questionnaire	X			X
Self-efficacy re: diet and exercise	X			X
Eating Stimulus Index	X			X
Perceived Stress Scale	X			

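### Aim 2 questionnaire scores get only unadjusted t-tests although each has its own baseline; adjusting for that baseline is a cheap, modest gain in precision and settles what is compared

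*Combined protocol and SAP*

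**What the plan says.** The Aim 2 text in section F (Data Analysis Plan) starts with univariate checks of baseline differences, distributions and outliers. It then gives one test, at a two-sided 0.05 level: "Student t-tests will be used to test for differences between intervention and control groups in change in weight (baseline to 12 wks". The object of that test runs on as "in change in weight (baseline to 12 wks) and in lifestyle habits". No covariate or regression model is mentioned anywhere.

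The substudy's secondary outcomes in section A include diet, physical activity, self-efficacy, the Eating Stimulus Index and "Readiness to change". Section F repeats all of these in its statement of Aim 2 except the last. The data collection overview in section C marks all five, for example "Self-efficacy re: diet and exercise", at both baseline and 12 weeks, and the Part A and Part B procedures confirm this for each arm. The Perceived Stress Scale is taken at baseline only and is not listed as an outcome.

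The baseline survey comes after allocation. Lifestyle women are offered it "After the person is consented into the main study and randomized to the lifestyle group", and of its timing the plan says: "This will occur either at the visit when the person is consented into the main study or at the baseline visit". They are asked again at 12 weeks, where entry requires "Participated in Part A Phase 1". Observation women are asked once: "This substudy opportunity for data collection at 2 time points will be offered to participants at the baseline visit".

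**The concern.** Two things are left on the table. First, the sentence in section F does not fix the quantity compared for the questionnaires. The baseline-to-12-weeks bracket is attached to weight, and lifestyle habits follow without one. Change scores and 12-week values can differ noticeably in precision, and which does better depends on a correlation seen only in the data, so the choice should not wait for the data. Readiness to change has no stated analysis.

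Second, neither t-test makes the best use of a baseline score that is already being collected. The substudy aims for 40 completers, section E warns of low power for small differences, and section G says the findings will inform later sample sizes. A baseline-adjusted model narrows the intervals at moderate correlations. Reporting the baseline-to-12-week correlation alongside it supplies one of the figures that such planning needs.

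**Working it through.** **Inputs.** From the documents: 20 women per arm, N = 40 (section F, sample size; section C, completer target); two-sided 0.05; two-sample t-test without covariates (section F). The documents give no effect size, SD, power or correlation for Aim 2, and 40 was chosen for Aim 1, so there is no Aim 2 figure to reproduce. Assumed: baseline-to-12-week correlation ρ of 0.4 to 0.7, normal scores, SD 1 at both visits and in both arms.

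**Variance per woman.**
- 12-week value: 1
- Change score: 2(1 − ρ)
- 12-week value adjusted for baseline: (1 − ρ²) × 37/36

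The factor 1 + 1/(N − 4) = 37/36 = 1.028 is the expected price of chance baseline imbalance. The adjusted model has 37 degrees of freedom instead of 38 (critical t 2.0262 instead of 2.0244).

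**95% CI half-width** = t × √(variance × 2/20). For ρ = 0.5 the adjusted model gives 0.75 × 37/36 = 0.771 and 2.0262 × √0.0771 = 0.563. Either t-test gives 2.0244 × √0.1 = 0.640. The ratio is 0.88.

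| ρ | Half-width: 12-week | change | adjusted | adjusted/change | adjusted/12-week |
|---|---|---|---|---|---|
| 0.4 | 0.640 | 0.701 | 0.595 | 0.85 | 0.93 |
| 0.5 | 0.640 | 0.640 | 0.563 | 0.88 | 0.88 |
| 0.6 | 0.640 | 0.573 | 0.520 | 0.91 | 0.81 |
| 0.7 | 0.640 | 0.496 | 0.464 | 0.94 | 0.72 |

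**Where the gain stops.** Let k = (2.0262/2.0244)² × 37/36 = 1.0296. The adjusted interval is narrower than the 12-week one when (1 − ρ²)k < 1, so ρ above about 0.17. It is narrower than the change-score one when k(1 + ρ)/2 < 1, so ρ below about 0.94. Simulation puts these limits at roughly 0.16 and 0.95.

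**Power at an assumed difference of 0.8 SD**, for ρ = 0.4/0.5/0.6/0.7: adjusted 76/80/86/93%, change 61/69/79/89%, 12-week value 69% throughout. In simulation at 20 per arm (ρ = 0, 0.3, 0.5 and 0.7) the adjusted test's type I error was 4.7 to 5.0%.

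**Skewed scores.** In a simulation of raw log-normal scores (log SD 0.7; latent ρ 0.4/0.5/0.7; a 0.8 SD shift on the log scale), the adjusted model with HC3 standard errors had power 60/64/79%, change 57/64/82%, and the 12-week value 59 to 60%. The advantage over change disappears at 0.5 and reverses at 0.7.

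**Baseline taken after allocation.** Suppose knowing the arm shifts the lifestyle group's baseline answers by s, with no effect on the 12-week score. The size of the bias is ρs for the adjusted model, s for a change score and 0 for a 12-week comparison. With s = 0.2 SD (assumed) and ρ from 0.4 to 0.7, that is 0.08 to 0.14 SD, 0.20 SD and 0.

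**The case against.** The strongest reply is that change most naturally governs both weight and lifestyle habits. Aim 2 runs over 12 weeks, and section G speaks of an impact on lifestyle changes. This stands. On that reading the relevant ratios are 0.85 to 0.94, a 6 to 15% narrower interval. The larger gains against a 12-week t-test apply only to the less likely reading.

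It also stands that ρ is assumed, that the gain can vanish on raw skewed scores, and that the adjusted model is exposed to arm-related baseline shifts that a 12-week comparison avoids. The exposure is real. The survey follows known allocation, it may fall at the baseline visit where lifestyle women are coached, and the order of survey and coaching is not stated. Surveying first removes the effect of coaching but not knowledge of the arm. Substudy entry also follows allocation, by a different route in each arm, so no analysis of these scores is fully protected by randomisation.

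A reader might infer more than this:
- **That the planned t-tests are invalid.** They are not: with equal SDs and no baseline shift they hold their error rate, and the loss is one of precision.
- **That self-efficacy and eating stimulus are left untested.** Section F names both in its Aim 2 statement, and a broad reading of lifestyle habits covers them. Only readiness to change is absent.
- **That weight needs the same treatment.** Section F defines weight as a change, and this point makes no claim about it.
- **That HC3 standard errors, a log-scale rule, mean imputation of missing baselines or Welch's test for weight are needed.** These are options. Their case rests on variance ratios, skewness and missing rates that the documents do not give.

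**Conclusion.** The point holds as one of efficiency and specification. Section F leaves the questionnaire comparison not fully defined, omits readiness to change, and does not use baseline scores that are already planned. At 20 per arm and assumed correlations of 0.4 to 0.7, adjustment narrows the 95% interval to 0.85 to 0.94 of the change-score width, or 0.93 to 0.72 of the 12-week width. It beats both t-tests over most of the plausible range of ρ. This rests on normal scores, equal SDs and 20 completers per arm; with strong skew the gain over change can vanish. Against a baseline shift the adjusted model is safer than a change score but not immune.

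Severity is modest. These are secondary outcomes of a pilot sized for Aim 1, sections E and F already admit limited power, and nothing here affects the feasibility conclusions.

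**What to change.** In section F, for each questionnaire score, including readiness to change:
- Fit a linear model of the 12-week score on arm and that score's own baseline. Report the adjusted arm difference with its 95% confidence interval.
- Report the baseline-to-12-week correlation for future planning.
- Show the unadjusted 12-week comparison as a sensitivity analysis, because a post-allocation shift in baseline answers does not bias it.

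In section C, state that the baseline substudy survey is completed before any baseline coaching.

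The cost is a few sentences and no new data. Each model spends one degree of freedom (about 3% in variance) and assumes a roughly linear relation with baseline. It accepts a bias of ρ times any arm-related baseline shift. Women may decline questions, so some may lack a baseline score; the adjusted model omits them, as a change score would, while the 12-week comparison keeps them.

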## **II. Background and Significance:**

Low-income and minority women are at increased risk for postpartum weight retention (i.e. retaining weight after pregnancy) and consequent persistent obesity. Women who have had children, especially racial/ethnic minority women who have had children, have 3 times the risk of obesity compared to women who have not had any children. Pre-pregnancy obesity is an important contributor to postpartum weight retention. Women who are obese pre-pregnancy are 3-5 times more likely to gain weight, rather than lose weight, in the postpartum period than non-obese women. Addressing maternal weight during this time is critical given that obesity places women at increased risk for poor health outcomes (e.g. cardiovascular disease) and their offspring at increased risk for obesity. Addressing maternal weight in the first year postpartum is essential given evidence that weight retained beyond this period is usually retained long-term and is an independent risk factor for obesity.

Effective interventions addressing postpartum weight retention in low-income and racial/ethnic minority women are urgently needed. Translation of evidence on weight loss to the postpartum period in a community setting is lacking, yet holds great potential. WIC is an ideal location to translate such evidence given that WIC, staffed by educators and registered dietitians (RDs), interacts regularly with women in the postpartum period, offering nutrition education and supplemental foods.

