### **B. Description of Population to be Enrolled:**

#### **Main study:**

We will be working with low-income, English or Spanish-speaking postpartum mothers enrolled in the Aurora WIC clinic. The Aurora WIC clinic serves predominantly minority women; nearly 70% of women are racial/ethnic minorities. To be eligible for WIC, women must be low-income or  $\leq 185\%$  of the poverty level.

This population was chosen because they are at high risk for obesity in the postpartum period and weight retention and prolonged obesity.

Inclusion criteria:

- Adult woman ( $\geq 18$  and  $< 50$  years old)
- Enrolled in WIC or with an infant enrolled in WIC;
- 3-12 months postpartum
- A pre-pregnancy BMI of 25 - 40 kg/m^2 (based on self-reported height and weight prior to pregnancy)
- Postpartum body mass index between 25 and 50 kg/m^2
- English- and/or Spanish-speaking
- Owns a mobile phone with texting functionality
  - In order to receive texts during the trial

Exclusion criteria:

- Health conditions impacting weight or ability to participate in a weight loss trial
  - Pregnancy or planned pregnancy in next 5 months
  - Any health problems or undergoing any treatments that might interfere with what participant eats or her ability to exercise
  - Medical provider recommendation to avoid exercise
- Plans to be in a different geographic area within the next 5 months
- Plans to stop coming to Aurora WIC in the next 5 months.
- Unable to give informed consent;
- Not able to read and understand English or Spanish at an 8th grade level.
- Not willing to create a Facebook account if they do not already have one.
- Asked to follow-up in  $< 3$  months at most recent WIC visit

Substudy:

The substudy will have 2 parts – Part A and B. Part A applies to the lifestyle group from the main study and will have 2 phases (1 and 2). This is split into 2 phases so that Phase 2 opportunity and the associated financial remuneration of Phase 2, is not known until the 12 week visit. We want a true assessment of the participation in the lifestyle intervention as it would be run in WIC, and thus do not want participants to stay in the intervention solely for the remuneration in the substudy. Part B applies to the observation group in the main study.

Part A Phase 1

Inclusion criteria:

- Participant in the lifestyle group in the Main study presenting for baseline visit

Exclusion criteria:

- None

Part A Phase 2

Inclusion criteria:

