## Study procedures:

### Main study:

In this randomized controlled study participants will be randomly assigned to either an observation group (control) or a Lifestyle group (intervention). Both groups will receive the following:

1. Two visits to the WIC office for data collection as described below (Baseline and at 12 weeks).
2. Study visit reminder calls and/or texts either or both ~1 week and ~1-3 days before baseline and the 12 week study visit.
3. A small gift (less than \$5 in value) at the baseline visit.

For each subject, the time from enrollment to study completion will be approximately 12-20 weeks, depending on timing of scheduling of the visits.

Baseline and 12 week study visits and parameters to be measured on all participants:

At the baseline study visit, we expect data collection to take < 30 minutes. We will collect data using a survey and anthropometric measurements.

- **Survey:** We will orally administer the survey (Appendix B) to participants to avoid literacy issues that are common in low-income populations. Survey questions will include the following:
  - a. Demographics: Maternal age, education level, race, ethnicity, marital status, employment status, number of children, age of youngest child (months), ages of children at home, and acculturation level. To measure acculturation, we will use an adapted version of the Spanish and English language-use subscales of the Bidimensional Acculturation Scale for Latinos. Each subscale contains 5 items about language use, with responses ranging from never (1) to always (5).
  - b. We will also ask about smoking, formula and breastfeeding, and whether the mother has been or is diabetic or prediabetic, mother's weight before her recent pregnancy, and whether she is currently participating in any weight loss programs or is pregnant.

- c. Contact information: We will ask for her name, address, phone numbers, email address, and contact information for someone we can call if we cannot reach the participant. We will ask her to identify the number she wants to receive texts and the email address where we send the Facebook invite, if she is in the Lifestyle group.
- **Anthropometrics:** Weight and height measured twice using WIC scales and stadiometer.

At the 12 week study visit, we expect data collection to take about 20 minutes, collecting anthropometric measurements and some survey data.

**Anthropometrics:** Weight and height measured twice using WIC scales and stadiometer.

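### The 12-week weight comparison is valid but makes no use of pre-pregnancy BMI, which the protocol itself calls prognostic; a pre-specified adjusted model would cost almost nothing

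*Combined protocol and SAP*

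**What the plan says.** Section IV.F (Aim 2) gives the whole efficacy analysis of weight in one sentence: "Student t-tests will be used to test for differences between intervention and control groups in change in weight (baseline to 12 wks"), two-tailed at 0.05. No covariate is named. The same paragraph plans a univariate look at baseline differences in demographic, lifestyle and infant feeding variables, but attaches no action to what it finds.

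The target size is given as "The sample size is 40 (20 intervention and 20 control"), with enrolment of up to 80 allowed. Section IV.C (Treatment assignment) randomises in blocks of 10 and names no stratification factor.

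Section II calls pre-pregnancy obesity an important contributor to weight retention and adds: "Women who are obese pre-pregnancy are 3-5 times more likely to gain weight, rather than lose weight, in the postpartum period than non-obese women". On time since delivery, it says only that, past the first year, "weight retained beyond this period is usually retained long-term".

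Eligibility (section IV.B) covers self-reported pre-pregnancy BMI of 25 to 40 kg/m² and women "3-12 months postpartum". The baseline survey (section IV.C, Study procedures) collects "age of youngest child (months") and the mother's weight before the recent pregnancy. Weight and height are measured at the same visit.

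**The concern.** The protocol identifies a baseline factor that it believes affects whether women gain or lose weight postpartum. It then admits women on both sides of that factor and uses it in neither the randomisation nor the analysis. In a trial of about 40 women the arms may well differ on it by chance. The unadjusted difference in weight change would then include whatever that imbalance contributes, and this could exaggerate an intervention effect or hide one.

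The baseline check does not protect against this. It leads to no action, and its listed categories do not clearly include pre-pregnancy weight. An adjustment added after an imbalance had been seen would be post hoc.

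What is at stake is modest but real. Section IV.G says the Aim 2 findings will help decide whether to evaluate the intervention on a larger scale and will inform sample size estimates. Those decisions will rest on the one allocation that is realised.

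**Working it through.** **The plan's own figure.** The total of 40 cannot be reproduced from a formula. Section IV.F says it was set for Aim 1 and gives no effect size, SD or power for weight.

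**1. Chance of a sizeable imbalance.** For a covariate in SD units and n per arm, the difference in means has standard error √(2/n). The chance of a difference above 0.5 SD in either direction is 2·[1 − Φ(0.5/√(2/n))].
- n = 20: 0.5/0.316 = 1.58, giving 11.4%.
- n = 40 (the enrolment ceiling): 0.5/0.224 = 2.24, giving 2.5%.

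**2. Is the t-test's error rate wrong?** This was simulated with 100,000 trials per scenario, a normal outcome, and one covariate explaining an assumed 10%, 25% or 40% of the variance in weight change (the documents give no figure).

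| 20 per arm | R² 0.10 | R² 0.25 | R² 0.40 |
|---|---|---|---|
| t-test, all randomisations | 5.0% | 5.0% | 5.0% |
| t-test, imbalance above 0.5 SD | 8.8% | 13.4% | 19.1% |
| Adjusted model, imbalance above 0.5 SD | 4.9% | 4.8% | 5.2% |

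Overall the planned test is sound. The problem is conditional on an imbalance having occurred.

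**3. Plausible size in kg.** Assumptions: half the women obese before pregnancy, 1 to 2 kg difference in 12-week change between obese and overweight women, SD of change 4 kg, 20 per arm.
- 95% range for the difference in proportion obese: ±1.96·√(0.25·2/20) = ±31 percentage points. At 40 per arm: ±22 points.
- Shift at the edge of that range: 0.31 × 1 to 0.31 × 2 = 0.31 to 0.62 kg.
- Half-width of the planned 95% CI: 2.024 × 4 × √(2/20) = 2.56 kg.
- Ratio: 0.31/2.56 = 0.12 to 0.62/2.56 = 0.24, so under a quarter.

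**4. Variance explained under those assumptions.**
- BMI alone: (1² × 0.25)/16 = 0.016 to (2² × 0.25)/16 = 0.063. Both lie below the smallest R² in the table, so the conditional false-positive rate would be below 8.8%.
- Adding months since delivery, uniform on 3 to 12 (SD 9/√12 = 2.60) at an assumed 0.1 to 0.3 kg per month: variance 0.07 to 0.61 kg². Total R² is (0.25 + 0.07)/16 = 0.02 to (1.00 + 0.61)/16 = 0.10.

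**5. Effect of adjustment on precision (20 per arm, two covariates, simulated).**
- R² = 0: interval about 3% wider. Check: √(37/35) × 2.028/2.024 = 1.03.
- R² = 0.02: about 2% wider.
- R² = 0.10: about 2.5% narrower.
- Break-even is at an R² of about 0.06.

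**The case against.** The strongest reply is that nothing is broken. Randomisation already makes the unadjusted comparison valid, and chance imbalance is part of the sampling error that the 5% level and the confidence interval cover. The concurrent control arm deals with natural postpartum change. A reader might infer that the plan inflates false positives. The documents do not support that: the error rate is 5% over all randomisations, and an imbalance is as likely to mask an effect as to mimic one. This part of the reply stands.

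A reader might also infer that the background treats months since delivery as a driver of weight course within the eligible window. It does not. It separates the first year from later and says nothing about change by month between 3 and 12 months. This also stands, so timing can enter only as a labelled assumption.

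The support for BMI has limits too. The 3-to-5-fold figure contrasts obese with all non-obese women, while this trial contrasts obese with overweight women. No difference in kg is given. Pre-pregnancy weight is self-reported, and it is taken at a baseline survey that follows randomisation; the screening form carries no identifiers. Adjustment for it will therefore be imperfect.

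Finally, weight change is a secondary outcome, the efficacy aim is called preliminary, section IV.E concedes limited power, and up to 80 women may be enrolled. These facts lower the importance of the point. They do not remove it. The protocol documents a prognostic factor, collects it and leaves it out of the analysis, although the estimate is meant to inform later planning.

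**Conclusion.** The point holds as a minor improvement and not as an error in the test. The planned t-test is valid. It does ignore a factor that the protocol calls prognostic, in a small trial with unstratified randomisation, where an imbalance above 0.5 SD on a given covariate has about an 11% chance at 20 per arm and 2.5% at 40.

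The likely effect is small: at most about 0.6 kg from pre-pregnancy BMI at the edge of its 95% imbalance range, less than a quarter of the interval's half-width. That rests on assumed values (SD 4 kg, a 1 to 2 kg contrast, half the women obese before pregnancy), none of which the documents give. Under the same modest effects adjustment does little for precision, from about 2% wider to 2.5% narrower. Its main benefit is that the estimate takes account of the imbalance that actually occurs, by a rule fixed in advance.

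**What to change.** In section IV.F, Aim 2:
- Make the main weight comparison a pre-specified linear model (ANCOVA) of 12-week weight, or weight change, on arm, with baseline weight and pre-pregnancy BMI as continuous covariates. Once baseline weight is in the model, the arm coefficient is the same for either outcome.
- Report the adjusted difference with its 95% CI, and keep the t-test as a supporting result.
- State that covariates will not be chosen from baseline significance tests.
- Age of the youngest child in months may be added, labelled as an assumption.
- Note that pre-pregnancy weight is self-reported.

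The cost is a sentence or two and no new data. With 20 per arm, the interval is about 3% wider if the two covariates predict nothing. A third uninformative covariate would bring this to about 5% (√(37/34) × 2.030/2.024 = 1.046).
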